7.11 Health Outcomes Relative to Costs

Information on health-care resource use will be combined with information on OS and quality of life to estimate the value associated with the addition of Lu-PSMA to enzalutamide in terms of the cost per QALY.

8 SAFETY REPORTING

8.1 Definitions

An ADVERSE EVENT (AE) is any untoward medical occurrence in a patient or clinical investigational participant administered a pharmaceutical product and which does not necessarily have a causal relationship with this treatment. An AE can therefore be any unfavourable or unintended sign (including an abnormal laboratory finding), symptom, or disease temporally associated with the use of a medicinal investigational product, whether or not considered related to the medicinal product (see below).

AEs include the following:

- All suspected adverse drug or device reactions
- All reactions from drug or device – overdose, abuse, withdrawal, sensitivity, toxicity or failure of expected pharmacological action (if appropriate)
- Apparently unrelated illnesses

- Worsening (severity, frequency) of pre-existing illnesses or symptoms
- Injury or accidents
- Abnormalities in physiological testing or physical examination that require clinical intervention or further investigation (beyond ordering a repeat examination)
- Laboratory abnormalities that require clinical intervention or further investigation (beyond ordering a laboratory test)
- Any untoward event that occurs after the protocol-specified reporting period which the Investigator believes may be related to the drug or device.

A SERIOUS ADVERSE EVENT (SAE) is any untoward medical occurrence that at any dose:

- results in death,
- is life-threatening (i.e. the participant is at risk of death at the time of the event),
- requires inpatient hospitalisation or prolongation of existing hospitalisation,
- results in persistent or significant disability or incapacity,
- is a congenital anomaly/birth defect,
- other important medical events which, in the opinion of the investigator, are likely to become serious if untreated, or as defined in the protocol

NOTES:

- i. The term “life-threatening” in the definition of “serious” refers to an event in which the patient was at risk of death at the time of the event; it does not refer to an event which hypothetically might have caused death if it were more severe.
- ii. Important medical events which may not be immediately life-threatening or result in death or hospitalization but which may jeopardize the patient or may require intervention to prevent one of the listed outcomes in the definition above should also be considered serious.

In Australia the following definitions are used for reporting of safety events;

- A SIGNIFICANT SAFETY ISSUE (SSI) is defined as a safety issue that could adversely affect the safety of participants or materially impact on the continued ethical acceptability or conduct of the trial. These events may be in addition to the current SAE/SADR/SUSAR reports and generally have a consequence related to patient safety within the current study protocol, which thus requires some type of amendment.
- An URGENT SAFETY MEASURE (USM) is one type of significant safety issue where sponsors or trial investigators act immediately to protect participants from an immediate hazard to their health and safety. USMs are often instigated before the TGA and HREC are notified. In these cases, it is strongly recommended that the sponsor contact the TGA within 24 hours of the measure being taken.

Examples include:

- a serious adverse event that could be associated with the trial procedures and that requires modification of the conduct of the trial
- a hazard to the patient population, such as lack of efficacy of an IMP used for the treatment of a life-threatening disease
- a major safety finding from a newly completed animal study (such as carcinogenicity)
- a temporary halt/termination of a trial for safety reasons
- recommendations of the Data Safety Monitoring Board, where relevant for the safety of participants, such as an increase in frequency or severity of an expected adverse reaction

- single case events (e.g. toxic epidermal necrolysis, agranulocytosis, hepatic failure) that lead to an urgent safety measure)

SSIs or USMs do not necessarily meet all criteria to be considered an SAE. For purpose of safety reporting, these events are to be reported as SAE with a note that this concerns an SSI or USM.

A SUSPECTED UNEXPECTED SERIOUS ADVERSE REACTION (SUSAR) is an SAE that is related to the drug or device and is unexpected, i.e. not listed in the investigator brochure or approved Product Information; or is not listed at the specificity or severity that has been observed; or is not consistent with the risk information described in the Participant Information Sheet and Informed Consent Form or elsewhere in the protocol. An event is causally related if there is a reasonable possibility that the drug [intervention] caused the AE, i.e. there is evidence to suggest a causal relationship between the drug and the event.

8.2 Recording Adverse Events

AEs will be recorded from the first dose of study treatment until 12 weeks after cessation of study treatment. The CTCAE v5.0 will be used to classify and grade the intensity of AEs after each treatment cycle. The worst grade will be recorded for each event. The investigator's assessment of attribution to study drug administration will also be collected.

8.3 Reporting of Serious Adverse Events (including SUSARs)

The investigator is responsible for reporting all SAEs (including SUSARs) occurring during the study to the NHMRC Clinical Trials Centre within 24 hours of investigational site staff becoming aware of the event according to the procedure documented in the Study Manual. SAEs must be reported up to 12 weeks from the end of Lu-PSMA study treatment or 30 days from the last dose of enzalutamide, whichever comes first.

The NHMRC CTC will be responsible for providing reports to the Lead HREC. The NHMRC Clinical Trials Centre will provide SUSAR reports and SAE line listings to Investigators for submission to Human Research Ethics Committees (HRECs) as required. The investigator must notify the local HREC as required.

The NHMRC Clinical Trials Centre will submit 'reportable safety events' to the TGA in Australia in time to comply with the requisite specified regulatory time windows (usually 7 days for fatal/life threatening events with an 8 day follow-up report, and 15 days for other SUSARs).

The following information will be recorded for each SAE:

- Event description including classification according to NCI CTCAE v5.0
- Reason for classification as an SAE (death, hospitalisation etc.)
- Severity/ worst grade
- Attribution to study intervention (Lu-PSMA only)
- Expectedness (listed in IB/product information)
- Action taken with study intervention (Lu-PSMA and enzalutamide or enzalutamide alone), including rechallenge (if done)
- Outcome of SAE, including end date if recovered

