5.1 Study Treatment

5.1.1 Lu-PSMA

The administered activity of Lu-PSMA is standardised at 7.5 GBq ($\pm 10\%$) for each treatment dose.

All participants on the experimental arm will receive 2 doses of Lu-PSMA on Days 15 (± 7) and 57 (± 7) unless there is unacceptable toxicity (See section 5.2). The first dose is administered 14 days (± 7 days) after starting enzalutamide.

Participants will undergo a repeat ⁶⁸Ga-PSMA PET/CT at Day 92 (± 7 days). ⁶⁸Ga-PSMA PET/CT at Day 92 allows sufficient time for central imaging review prior to determining a participant's suitability for further doses of Lu-PSMA. This scan should be performed no later than Day 99 (minimum 14 days before Day 113 Lu-PSMA treatment) to ensure adequate time is available for Lu-PSMA order and delivery.

Day 92 ⁶⁸Ga-PSMA PET/CT scans will be reviewed centrally. Participants will proceed with doses 3 and 4 at Days 113 (± 7) and 169 (± 7) if volume and intensity of residual PSMA avid disease is deemed adequate for target Lu-PSMA therapy on this scan, and if clinically appropriate (including meeting all safety criteria). Treatment will be administered to a maximum of 4 cycles, at a minimum interval of 6 weeks (42 days), subject to availability.

Lu-177 is required to be ordered at least 10 days before the planned administration for each cycle.

Lu-PSMA will be administered by slow intravenous injection. SPECT/CT imaging encompassing the neck, chest, abdomen and pelvis will be performed 24 hours (\pm 4 hours) after Lu-PSMA administration. See Nuclear Medicine Manual for Lu-PSMA manufacturing, quality control, and administration details.

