c. Baseline tissue biopsy (optional) may occur any time after patient consents (pre- or post-randomisation), but prior to commencing study treatment. Refer to the Biospecimen Sampling Manual for details.
5. PSA progression and radiological progression may occur at different times. If so, then ⁶⁸Ga-PSMA PET/CT, ¹⁸F FDG PET/CT, translational research blood collection and tissue biopsies (optional) are only required to be completed at first documented progression (either PSA or radiological, whichever occurs first).
6. Imaging must include a CT of the chest, abdomen and pelvis, and a radio-isotope whole body bone scan (WBBS). If screening FDG PET imaging includes a diagnostic CT, then a separate baseline CT is not required. 12-weekly imaging with CT and WBBS should continue until radiological progression is documented per RECIST 1.1 or PCWG3 (see section 7.2), even if new anticancer treatment is commenced earlier.
7. Adverse events categorised and graded according to CTCAE v5.0 and should continue to be recorded until 12 weeks after the study treatment ends.
8. For Day 15 assessments a window of +7 days only is permitted, with the exception of the Day 15 ⁶⁸Ga-PSMA PET which has a -5/+7 day window
9. If screening medical oncologist assessment, blood tests and PSA were completed within 7 days prior to randomisation, then they do not need to be repeated.
10. Baseline HRQL forms and Fear of Cancer Progression Short Form can be completed within 7 days pre- or post-randomisation, prior to commencing study treatment.

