6.3 End of Treatment and 30 - 42 day Safety Assessment

An end of treatment and safety assessment should be performed 30 to 42 days, and 84 days after the last dose of study treatment to include any adverse events occurring within 12 weeks after the last dose of study treatment. In the event of unresolved toxicity participants should continue to be followed.

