12 STUDY TREATMENT SUPPLY AND ACCOUNTABILITY

12.1 *Study Treatment*

The investigational agents are enzalutamide and ^{177}Lu PSMA-617.

PSMA-617 is a small molecule ligand that binds to the extra-cellular domain of the prostate-specific membrane antigen. Each vial is supplied with a chemical purity $\geq 95\%$. Lutetium-177 (^{177}Lu) is a nuclear reactor-produced radiometal with a half-life of 6.7 days. Its decay mode is beta Max 0.5 MeV, average beta 0.13 MeV and gamma 208 keV (11% abundance). It is supplied in the chemical form of Lutetium Chloride (LuCl_3) in 0.04 M HCl with a radionuclide and radiochemical purity of $>99\%$.

No carrier added (n.c.a.) ^{177}Lu and PSMA-617 will be provided as clinical trial stock. The final product ^{177}Lu -PSMA-617 will be compounded on site according to the Nuclear Medicine Manual by a qualified radiopharmacist or radiochemist. Quality control will be performed with HPLC prior to release of product. The study drug will be administered to eligible participants under the supervision of the nuclear medicine investigator or identified co-investigators.

12.2 *Control Treatment*

Enzalutamide is an androgen receptor inhibitor. It is provided as liquid-filled soft gelatine capsules each containing 40 mg enzalutamide for oral administration. Each carton contains 112 capsules. The inactive ingredients are caprylocaproyl polyoxylglycerides, butylated hydroxyanisole, butylated hydroxytoluene, gelatine, sorbitol sorbitan solution, glycerin, purified water, titanium dioxide, and black iron oxide.

Cartons of enzalutamide should be stored below 25°C (77°F) in a dry place.

Full details on product handling information are provided in the Product information, Investigator Brochure and Pharmacy Manual.

12.3 *Drug Accountability*

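### SAE reporting ends at the earlier of two dates, so it can close during enzalutamide treatment in the Lu-PSMA arm but never in the control arm

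*Protocol*

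**What the plan says.** Section 8.3 begins with a general duty: "The investigator is responsible for reporting all SAEs (including SUSARs) occurring during the study". The next sentence sets a time limit on that duty, which runs "up to 12 weeks from the end of Lu-PSMA study treatment or 30 days from the last dose of enzalutamide, whichever comes first".

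Three other places set the window for adverse events, and all use 12 weeks after study treatment, without distinguishing the arms:
- Section 8.2: "AEs will be recorded from the first dose of study treatment until 12 weeks after cessation of study treatment".
- Section 6.3, on the post-treatment safety visits: "any adverse events occurring within 12 weeks after the last dose of study treatment".
- Note 7 to the schedule in section 6.1: adverse events "should continue to be recorded until 12 weeks after the study treatment ends".

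Under section 5.1.1 Lu-PSMA is limited to four doses. Two are planned for all experimental-arm men, on Days 15 and 57. Two more, on Days 113 and 169, depend on the Day 92 scan. Under sections 5.1.2 and 5.7 enzalutamide has no fixed end in either arm and may continue after PSA progression alone. Section 13.2 tabulates SAEs by treatment allocation.

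The list of SAE data items in section 8.3 includes "Attribution to study intervention (Lu-PSMA only"), while section 12.1 states: "The investigational agents are enzalutamide and" the Lu-PSMA product.

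**The concern.** Safety is part of the trial's stated aim, and SAEs are to be compared by arm. A fair comparison needs the same reporting rule in both arms. Here one of the two closing dates exists only for men who receive Lu-PSMA, and the earlier date governs. A man doing well on the combination therefore leaves SAE reporting while still on study treatment. A control man doing equally well does not. Fewer experimental-arm SAEs would reach the coordinating centre and the SAE table, even if the true frequency were the same in both arms.

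The rule also shortens coverage after an early stop. A man who stops both drugs soon after a Lu-PSMA dose has 30 days of SAE reporting, although section 6.3 schedules a Day 84 safety visit to capture events up to 12 weeks.

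**Working it through.** **Closing dates.** 12 weeks = 84 days.
- Two doses: 57 + 84 = Day 141.
- Four doses: 169 + 84 = Day 253.
- Both drugs stopped on Day 57: SAE reporting closes at 57 + 30 = Day 87, but adverse event recording continues to 57 + 84 = Day 141.
- Control: always last enzalutamide dose + 30 days.

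These dates are nominal. Lu-PSMA doses have a window of ±7 days, and section 5.7 tolerates long Lu-PSMA delays, which would move closure later.

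**Size.** The protocol gives neither an enzalutamide treatment duration nor an SAE rate, so there is no figure of its own to reproduce. As an illustration, assume time on enzalutamide T is exponential with a 5-month median in both arms. The 5 months is the control median PSA PFS in section 13.1, used as a proxy. Equal medians isolate the effect of the rule from any treatment effect.

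- 5 × 30.4375 = 152.2 days; λ = ln 2 / 152.2 = 0.004554 per day; mean T = 1/λ = 219.6 days.
- Control mean window: 219.6 + 30 = about 250 days.
- Experimental mean window, with closure day c: E[min(T + 30, c)] = 30 + (1 − exp(−λ(c − 30)))/λ.
  - c = 141: 30 + 219.6 × (1 − 0.603) = about 117 days.
  - c = 253: 30 + 219.6 × (1 − 0.362) = about 170 days.
- Share still on enzalutamide at closure, exp(−λc): 53% at Day 141 and 32% at Day 253.

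The experimental window is thus 53% (two doses) or 32% (four doses) shorter than the control window.

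**Sensitivity to duration.**

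| Assumed median, control / experimental | Control window | Experimental, 2 to 4 doses | Experimental if not cut by the Lu-PSMA limb |
|---|---|---|---|
| 5 / 5 months | 250 days | 117 to 170 days | 250 days |
| 5 / 8 months (5 / 0.625, the planning hazard ratio) | 250 days | 125 to 195 days | 381 days |
| 8 / 8 months | 381 days | 125 to 195 days | 381 days |

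**Effect on the SAE table.** Assume the same constant true SAE rate r in both arms and 5-month medians. The expected share of men with at least one reported SAE is 1 − E[exp(−r × window)]. At r = 0.5 per person-year this is 26% in control, against 15% (two doses) to 20% (four doses) in the experimental arm. With 160/2 = 80 men per arm, that is about 21 men against 12 to 16. For r from 0.25 to 1.0 per person-year, the spurious difference runs from about 4 points (14.8% against 10.9%) to about 15 points (42.5% against 27.1%).

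**The case against.** Four points can be made for the plan.

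1. *Recording and reporting are different duties.* Recording adverse events on the CRF and reporting SAEs to the coordinating centre may have different windows, so sections 8.2 and 8.3 need not contradict each other merely because their periods differ. That is fair. The stronger conflict is inside 8.3, between all SAEs during the study and a cut-off that can fall during study treatment. Reading the second sentence as limiting the first removes that conflict, but leaves a limit that depends on the arm.

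2. *Late serious events are not lost.* A reader might infer that late SAEs of the combination vanish and that the whole safety comparison is biased. The documents do not support this. SAEs are a subset of adverse events, which section 8.2 records in both arms until 12 weeks after treatment with worst grade and attribution. Section 6.2.6 collects hospitalisations, and deaths enter overall survival. What closes early is the SAE report, and with it the SAE table.

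3. *Rates need not be biased.* A reader might also infer that SAE rates are understated. The cut keeps the Lu-PSMA period plus 12 weeks and removes later enzalutamide-only time. A rate per unit of reporting time could therefore move either way.

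4. *Enzalutamide causality is not excluded.* The attribution item might suggest that an SAE caused by enzalutamide cannot be classed as related or as a SUSAR. That goes too far. Section 8.1 defines a SUSAR by relation to the drug, without restriction to Lu-PSMA, and section 8.2 collects attribution to study drug for all adverse events. What stands is that the item's restriction does not fit sections 8.1, 8.2 and 12.1.

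The safety analysis is also principally descriptive, and the primary endpoint and power are untouched.

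**Conclusion.** The rule in section 8.3 is wrong as written. The asymmetry follows from the dates alone and needs no assumption: only experimental-arm men can leave SAE reporting while still on study treatment, nominally at Day 141 or Day 253. Men who stop enzalutamide before the Lu-PSMA limb closes are governed by the 30-day limb, as control men are.

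The consequence is limited to SAE reports and the by-arm SAE tabulation, where experimental-arm counts and proportions are understated. The size depends on the assumed exponential durations, the assumed constant SAE rates and the number of Lu-PSMA doses given. PSA PFS is probably a short proxy for time on enzalutamide, since PSA progression alone does not stop treatment. A longer duration would widen the gap.

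The attribution item is a separate, smaller inconsistency in the same section.

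**What to change.** Replace the earlier-of-two-dates rule in section 8.3 with one rule for both arms, tied to the last dose of any study treatment. The natural choice is the 12-week window already in sections 8.2 and 6.3 and schedule note 7, which makes all four places agree. The minimum change is to let the later of the two existing dates govern. That keeps reporting open throughout enzalutamide in both arms, but post-treatment coverage would still differ between arms for men whose last Lu-PSMA dose was recent.

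Change the SAE attribution item to record attribution separately for Lu-PSMA and for enzalutamide.

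The cost is one sentence, one CRF field and somewhat more SAE forms. No extra visits are needed, because the Day 84 post-treatment assessment is already scheduled for both arms.

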5 TREATMENT PLAN

The experimental intervention in this trial is the combination of enzalutamide plus Lu-PSMA whilst the parallel arm is enzalutamide alone.

Participants in both groups are treated with a LHRHA (or surgical castration), as per standard of care. Androgen deprivation is to be given continuously in this trial. Intermittent androgen deprivation will be classified as a protocol violation. The dosing schedule for each treatment group is described in Table 1.

Table 1: Study Treatments

Agent(s)	Dose	Route	Duration
Enzalutamide	160 mg (four 40 mg capsules)	Orally	Daily until participant is no longer clinically benefiting, or experiences unacceptable toxicity
Lu-PSMA and Enzalutamide	7.5 GBq 160 mg (four 40 mg capsules)	IV Orally	All participants receive Lu-PSMA doses 1 and 2 (Days 15 and 57) unless unacceptable toxicity per section 5.2 of protocol. Doses 3 and 4 (Days 113 and 169) will be given following result of ⁶⁸ Ga-PSMA PET/CT at Day 92. Daily until participant is no longer clinically benefiting, or experiences unacceptable toxicity

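### The SAE stop rule in section 8.3 takes the earlier of two dates, so a combination-arm man who stays on enzalutamide more than 12 weeks after his last Lu-PSMA dose leaves 24-hour SAE reporting while still on study treatment; a control man never does

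*Protocol*

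**What the plan says.** Section 8.3 opens with a general duty: "The investigator is responsible for reporting all SAEs (including SUSARs) occurring during the study", to the coordinating centre within 24 hours of site awareness. The same paragraph then sets the end of reporting at "12 weeks from the end of Lu-PSMA study treatment or 30 days from the last dose of enzalutamide, whichever comes first".

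The two drugs have very different durations.

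- **Lu-PSMA** (sections 5 and 5.1.1) is finite. Doses 1 and 2 are planned for Days 15 and 57. Doses 3 and 4, on Days 113 and 169, depend on the Day 92 PET/CT. There are at most four cycles.
- **Enzalutamide** (section 5, Table 1) is given in both arms: "Daily until participant is no longer clinically benefiting, or experiences unacceptable toxicity". Under section 5.7, PSA progression alone does not end treatment.

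Enzalutamide is not treated as mere background. Section 12.1 begins "The investigational agents are enzalutamide and" and then names the Lu-PSMA compound.

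Non-serious recording has a different end. Section 8.2 states: "AEs will be recorded from the first dose of study treatment until 12 weeks after cessation of study treatment". Note 7 to the section 6.1 schedule says that adverse events "should continue to be recorded until 12 weeks after the study treatment ends", and section 6.3 plans post-treatment visits "to include any adverse events occurring within 12 weeks after the last dose of study treatment". None of these three differs by arm.

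**The concern.** Taking the earlier of two dates lets the short treatment close the window for the long one. Only combination-arm participants have a Lu-PSMA date, so only they can leave SAE reporting while still taking a study drug. The same rule can also shorten the Lu-PSMA follow-up that its own first limb sets at 12 weeks.

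The aim (section 2) includes the safety of adding Lu-PSMA to enzalutamide. Section 13.2 tabulates SAEs by treatment allocation, and under section 14.3 the independent committee monitors key safety endpoints. Serious events on continuing combination-arm treatment would no longer have to reach the coordinating centre within 24 hours, while the same events on continuing control treatment would.

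**Working it through.** The protocol gives no figure for the length of the SAE window, so there is none to reproduce. The check is date arithmetic on the rule.

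**Inputs.** L = day of last Lu-PSMA dose, planned as 57 or 169 (sections 5 and 5.1.1). E = day of last enzalutamide dose, open-ended (section 5). Tails: 84 days after Lu-PSMA and 30 days after enzalutamide (section 8.3).

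**Closing day.**
- Control: E + 30.
- Combination: the smaller of L + 84 and E + 30.

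**What follows for any E.**
- If E > L + 84, the combination window closes while the man is still on enzalutamide.
- If E > L + 54, it closes E − L − 54 days earlier than for a control man with the same E.
- If E < L + 54, it matches the control window, but the 12-week Lu-PSMA follow-up loses L + 54 − E days.

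For equal E, the combination window is therefore equal or shorter, never longer.

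**Planned days.**
- Two doses: 57 + 84 = Day 141. With the ±7-day dosing window, Day 134 to 148.
- Four doses: 169 + 84 = Day 253. With the window, Day 246 to 260.

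**Example: enzalutamide to Day 365.**

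| | SAE reporting ends | On-treatment days not covered | Shorter than control by |
|---|---|---|---|
| Control | 365 + 30 = Day 395 | 0 | – |
| Combination, two doses | Day 141 | 365 − 141 = 224 | 395 − 141 = 254 |
| Combination, four doses | Day 253 | 365 − 253 = 112 | 395 − 253 = 142 |

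AE recording under section 8.2 would run to 365 + 84 = Day 449 in either arm.

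**Example: enzalutamide stopped on Day 169, the day of dose 4.** The window closes on 169 + 30 = Day 199. The Lu-PSMA limb alone would run to Day 253, so 54 days of it are lost.

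**How many men might be affected (illustration).** The protocol gives no treatment durations. Assume exponential time on enzalutamide with median m months and a month of 30.4375 days. The share still on treatment at closing day c is 0.5^(c / (30.4375 m)), with c equal to 4.63 months for Day 141 and 8.31 months for Day 253.

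| Assumed median | Still on enzalutamide at Day 141 | At Day 253 |
|---|---|---|
| 5 months | 53% | 32% |
| 8 months | 67% | 49% |
| 12 months | 77% | 62% |

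The 5 months is the control median PSA PFS in section 13.1, and 8 = 5 / 0.625 is the value implied by the target hazard ratio. Neither is a treatment duration, hence the range.

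**The case against.** The case on the other side has four parts.

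**The general duty covers it.** A site could read the opening sentence as the on-treatment obligation and the next sentence as setting only the tail afterwards. That fits the text poorly, because a tail that starts from the end of Lu-PSMA and takes the earlier date can expire before enzalutamide ends. The specific stop sentence limits the general one. Reading the Lu-PSMA limb as the whole combination regimen does not work either, since enzalutamide has its own limb. The later date may have been intended, but the protocol does not say so.

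**Different duties may have different windows.** This stands. Sections 6.1, 6.3 and 8.2 govern AE recording, while section 8.3 governs expedited reporting. A reader might infer that a 30-day enzalutamide tail is wrong because AEs are recorded for 12 weeks, but nothing in the protocol shows that. The fault is the choice of the earlier date.

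**The events are not lost.** This largely stands, and a reader should not infer that serious events vanish from the trial. They are still recorded as graded AEs (section 8.2), and later events thought related still count as AEs (section 8.1). Hospitalisations go on a CRF (section 6.2.6, which states no collection period), and deaths are captured in survival follow-up (sections 6.1 and 7.7). Significant safety issues and urgent safety measures are to be reported as SAEs with no stated end date (section 8.1). None of these replaces an individual 24-hour report with its SAE record.

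**Lu-PSMA may be delayed.** Section 5.7 requires discontinuation for treatment-related adverse events only when a delay exceeds 16 weeks. A dose 4 given 16 weeks late moves the closing day to 253 + 112 = Day 365. The gap then starts later but remains for men who continue beyond it.

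**Conclusion.** The rule is wrong as written, and no other section cures it. At planned days, required 24-hour SAE reporting ends at about Day 141 or Day 253 for combination-arm men still on enzalutamide, and never ends on treatment for controls. This needs only the protocol's dates. It does not apply to every combination-arm man: he must stay on enzalutamide more than 12 weeks after his last Lu-PSMA dose. The share who do is not known, and the 32% to 77% above rests on assumed exponential durations.

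A reader might go further and infer that the SAE table will undercount the experimental arm by some definite amount. The documents do not support that.

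- Section 13.2 does not say which records feed the table. It calls the safety analysis principally descriptive and specifies no SAE test.
- The protocol gives neither SAE rates nor time on treatment.
- The direction is fixed only for equal enzalutamide duration. A control man who stops on Day 169 is covered to Day 199, while a four-dose combination man who continues to Day 365 is covered to Day 253. If combination-arm men stay on enzalutamide longer, or dose 4 is late, the arm totals need not favour the combination.

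The supported conclusion is unequal ascertainment through expedited reporting, plus a shortened Lu-PSMA tail for men who stop enzalutamide early. It is a drafting fault in safety reporting, worth correcting, and does not touch the primary endpoint or its analysis.

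**What to change.** In section 8.3, replace *whichever comes first* with *whichever comes last* and state the coverage in full, for example: *In both groups, SAEs are reported from the first dose of study treatment, throughout all study treatment, and until the later of 12 weeks after the last Lu-PSMA dose and 30 days after the last enzalutamide dose. SAEs after that time are reported if the investigator considers them related to study treatment.* This closes the on-treatment gap and restores the full 12 weeks after Lu-PSMA.

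Optionally, use a single tail of 12 weeks after the last dose of any study treatment in both arms, to match sections 6.1, 6.3 and 8.2. That adds 84 − 30 = 54 days of SAE reporting after enzalutamide. It is an alignment, not part of the correction.

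If the trial is under way, send a site notice asking for serious events already on AE forms that fell outside the old window to be reported as SAEs.

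The cost is one amended sentence and the notice. No new visits are needed, because section 6.3 already plans assessments at 30 to 42 days and at 84 days after the last dose. The downside is more SAE reports to process from men on long-term enzalutamide.
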